3.3.3 Multivariate analysis

An adjusted survival analysis will be performed with treatment group and covariates, listed below:

Characteristic	Categories
Age (years)	<= 75, >75 or <=median, >median
Preexisting diabetes at baseline	Yes, No
History of ASCVD	Yes, No

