1.3.3 Randomization and blinding

The randomisation list was centralised and generated by the Biostatistics department of the Hospices Civils de Lyon. Randomisation was stratified on the centre, to ensure a balanced distribution of confounding factors between arms and between centres. After the run-in period, investigators were need to connect to the CSOnline electronic case report form of the study and randomize their patients. Treatment was automatically assigned following the pre-established randomization list. The allocation ratio was 1:1 between the two groups.

Treatment vials were indistinguishable, therefore, this is double blinded study.

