1.3.4 Sample size determination

Assuming the following conditions:

- An annual event probability of events of 0.18 in the placebo arm (corresponding to an incidence of 19.84 per 100 person-years)
- A 30% reduction of this annual event probability in the spironolactone arm (active treatment), hence a probability of 0.126 (corresponding to an incidence of 13.46 per 100 person-years)
- A statistical power of 80% ($\beta = 20\%$)
- A bilateral test with a type-1 error rate α of 5%
- A premature study discontinuation rate (early drop-out) of 10%

A total number of **750 randomised patients (375 per arm)** to follow over 2 years in average is required to analyse the treatment effect with an exponential survival model. Considering early drop-out of 10% before randomisation, **825 patients** should be included at run-in phase.

[figure not shown]

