3.3.2 Formal analysis

Main analysis

Experimental treatment will be compared using the statistical framework of proportional hazards survival model adjusted on treatment group (spironolactone versus placebo) and stratified or adjusted by centre (randomisation stratification variable). The outcome is described in Section 3.3.1. The proportionality assumption will be assessed by analysing Schoenfeld residuals and examining log-log survival plots. The Efron method for ties and p-value based on the Wald statistic will be used. The event rates, p-value, HR, and 95% confidence interval will be reported.

In case of evidence of non-proportionality, a cautious interpretation of the model will be encouraged, and a weighted (Kaplan-Meier or Cox) or a parametric model event rate estimate will be emphasised.

Kaplan-Meier estimates of the cumulative proportion of patients with event will be calculated and plotted, for the composite endpoint and for each event types of the primary endpoint. The plot will include the number of subjects at risk for each treatment group over time.

Depending on the heterogeneity of the center effect and conditional on a sufficient number of patients by centre, a frailty proportional hazard regression [4, 5, 6] could be fitted, with the centre as random effect and treatment group as fixed effect. Random effect is used to account for correlation between observations within each centre and assumes a single hazard baseline function per centre.

If the number of randomised patients per centre is too low, they will be clustered according to their similarity in ARDS patients, or the number of included patients (for example “Limoges” vs. “others”) in 2 or more groups in order to sustain the hypothesis .

If no heterogeneity is observed, an unadjusted on centre Cox proportional hazard regression will be fitted.

Component of the primary endpoint:

The contribution of each component of the primary endpoint to the overall treatment effect will be examined. The first event of each given type of event will be included, irrespective of any preceding non-fatal event of a different type. Consequently, the sum of the number of patients with events in the component analysis will be larger than the number of patients with composite events. Methods similar to those described for the primary analysis will be used to separately analyse the time from randomisation to the first occurrence of each component of the primary composite endpoint.

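### The main Cox model in SAP 3.3.2 uses treatment and centre only; adding age, diabetes and ASCVD history before unblinding would recover a modest amount of power at little cost

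*SAP*

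**What the plan says.** Section 3.3.2, in the part on the main analysis, specifies a "proportional hazards survival model adjusted on treatment group (spironolactone versus placebo) and stratified or adjusted by centre". Centre is the only stratification factor at randomisation (1.3.3), and the general rule in 3.1 is to adjust for that factor alone. Section 3.3.2 also allows centre to be grouped, modelled as a frailty, or left out if no heterogeneity is seen. In that last case the deciding test would carry no baseline covariate at all.

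Section 3.3.3 then describes a second model: "An adjusted survival analysis will be performed with treatment group and covariates". Its list is age (split at 75 or at the median), pre-existing diabetes and history of ASCVD. The section does not say whether centre stays in this model.

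Age, diabetes and history of cardiovascular disease are among the baseline characteristics in 3.2.1. Diabetes and the separate cardiovascular history items are also eligibility variables in 1.3.6. The sample size in 1.3.4 takes no credit for covariate adjustment.

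**The concern.** In a Cox model, leaving out baseline factors that predict the outcome moves the estimated hazard ratio towards 1 relative to the conditional effect and costs some power. Here the SAP has itself picked three such factors and plans to fit them, but outside the model that decides the trial.

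Two features make a small gain worth having. The design has little reserve above 80% power. And the win ratio, the key secondary endpoint, is tested only if the primary p-value is below 0.05 (3.4.1), so power lost on the primary endpoint is also lost there. Eligibility is mixed, including structural heart abnormality, diabetes, established cardiovascular disease and raised CRP, so some spread in prognosis is plausible. The SAP does not quantify it.

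**Working it through.** **Inputs from the SAP.** "An annual event probability of events of 0.18 in the placebo arm"; a 30% reduction, "hence a probability of 0.126"; "A bilateral test with a type-1 error rate α of 5" per cent; "A statistical power of 80" per cent (all 1.3.4). "The allocation ratio was 1:1 between the two groups" (1.3.3). 750 patients "to follow over 2 years in average is required to analyse the treatment effect" (1.3.4).

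**Step 1: reproduce the plan's figure.**
- Hazards: −ln(1 − 0.18) = 0.1984 and −ln(1 − 0.126) = 0.1347 per year. HR = 0.1347/0.1984 = 0.679, and ln HR = −0.388.
- Events (Schoenfeld): 4 × (1.960 + 0.842)² / 0.388² ≈ 209.
- Two-year risks: 1 − 0.82² = 0.3276 and 1 − 0.874² = 0.2361; mean 0.2819.
- N = 209/0.2819 ≈ 742. Freedman's formula and two exponential-model formulas give 758 to 763, so the stated 750 reproduces.
- Power at 750: expected events 750 × 0.2819 = 211.4; Φ(√(211.4/4) × 0.388 − 1.960) = 80.5%.
- With 10% loss spread over 2 years: expected events about 201, power about 78.5%. The figure of 750 therefore holds without loss after randomisation.

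**Step 2: set up the comparison.** Each simulated trial had 750 patients, 1:1 allocation, 2 years of follow-up and a two-sided 5% Wald test. Treatment alone was compared with treatment plus three binary covariates. The covariate prevalences (40%, 45%, 55%) and a common covariate HR of 1.25 to 2.0 are assumptions. In each scenario the baseline hazard and the conditional treatment effect were solved so that the marginal 2-year risks stay at 0.3276 and 0.2361. This keeps the treatment effect equal to the one the SAP planned on. There were 15,000 trials per scenario.

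**Step 3: power.**

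| Covariate HR (each) | No loss: without → with | Gain (points) | 10% loss: without → with | Gain (points) |
|---|---|---|---|---|
| 1.25 | 80.1% → 80.3% | 0.2 | 77.6% → 78.0% | 0.4 |
| 1.5 | 80.1% → 81.5% | 1.4 | 77.7% → 79.6% | 1.8 |
| 1.75 | 79.6% → 82.5% | 2.9 | 78.2% → 80.9% | 2.7 |
| 2.0 | 80.6% → 84.7% | 4.2 | 78.3% → 83.1% | 4.8 |

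Gains are taken from unrounded powers. The Monte Carlo standard error of each gain is at most about 0.2 points.

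**Step 4: the same gains as events.** By normal approximation the relative information is ((1.960 + z_with)/(1.960 + z_without))², where z is the normal quantile of the power. Without loss this is 1.005, 1.036, 1.078 and 1.119. On a base of 209 events that is worth about 1, 8, 16 and 25 extra events.

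**Step 5: type I error and estimate.** Under the null (4,000 trials per scenario, 10% loss), type I error was 4.9% without and 5.0% with the covariates at covariate HR 1.5, and 5.5% and 5.4% at 2.0. Adjustment does not inflate it. At covariate HR 1.5 the average estimated HR was about 0.68 without and 0.67 with the covariates.

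**Limits.** No centre term was simulated. Age was binary, so any further gain from continuous age is not measured.

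**The case against.** The strongest reply is that nothing here is wrong. Centre is the only stratification factor, the SAP adjusts for it, the sample size assumes no covariates, and 3.3.3 already pre-specifies a model with exactly these three factors. That stands: the current main analysis is valid, and the choice lies between two acceptable models.

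Several stronger readings are tempting and are not supported.

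- A reader might infer that leaving out the covariates takes the trial below its planned power. If 0.679 is entered as the conditional hazard ratio, simulated power without covariates falls to 76.9% or 73.6%, depending on the assumed covariate effects. But the SAP derives 0.679 from event probabilities for whole arms, so it is a marginal effect. Calibrated to those probabilities, the model without covariates has about 80%, as planned.
- A reader might infer that chance imbalance compromises the primary test. Under randomisation it does not; it is already part of the test's stated error.
- A reader might take these three factors to be the strongest predictors of events. The SAP gives no effect sizes, and 3.3.4 lists other candidates such as heart failure hospitalisation, low ejection fraction and dialysis vintage.

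Other objections stand in part. Section 1.3.5 lets follow-up be extended and ends the study on events, and the quality-of-life plan speaks of 4 years on average. Final power may therefore differ from the 2-year planning figure, although the SAP states no event target. If the covariates are weak the gain is close to nil. ASCVD history is not defined, missing data are not replaced by default (3.1), and 3.2.1 refers to a database already frozen when the SAP was finalised. These add work to the fix but do not remove the gain.

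**Conclusion.** The point holds as a modest efficiency improvement. The gain is about 0.2 to 4.2 points of power without loss and 0.4 to 4.8 points with 10% loss, across covariate hazard ratios of 1.25 to 2.0. Under 10% loss, power returns above 80% only at covariate hazard ratios of 1.75 or more. The direction does not depend on the assumptions as long as the covariates predict the outcome; the size depends on them entirely. It is neither an error in the SAP nor evidence of an underpowered design.

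**What to change.** Before unblinding, make the main model in 3.3.2 a Cox model with treatment, the centre term as planned, age as a continuous variable, diabetes and ASCVD history. At the same time:

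- define ASCVD history from the eligibility items already collected (1.3.6);
- state a simple rule that keeps patients with a missing covariate in the ITT analysis, for example the overall mean for age and a separate category for a missing yes/no factor;
- state that the main hazard ratio is conditional on these covariates;
- report the model with treatment and centre alone alongside it.

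If the sponsor keeps the present main model, 3.3.3 still needs one fixed form for age, a definition of ASCVD history and a statement on whether centre is included.

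No new data are needed. The cost is SAP wording and a little programming, a conditional hazard ratio slightly further from 1 (about 0.67 against 0.68 at covariate HR 1.5), and a late change to the primary model. That change is legitimate only while the treatment code is still blinded.

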3.3.4 Subgroup analysis

Conditional to the number of events in each subgroups, the primary composite endpoint will be analysed for the characteristics listed in paragraph 3.3.3 Multivariate analysis

A test of interaction between randomised treatment group and the subgroup variable will be performed in each survival model, including as covariates: treatment group, the relevant subgroup variable and the interaction between treatment and the subgroup variable. In addition to the number and percent of patients with event, the event rate estimate, HR with 95% confidence interval for each subgroup and the interaction will be presented. HRs with confidence intervals will be presented in a forest plot, also including the event rate.

Other categories for subgroup analyses of the primary endpoint

Characteristic	Categories
IMC (kg/m ²)	<= ,>30 or <23 ,23-30 >30 or according to quantiles
history of HF hospitalisation	Yes, No
EF < 40%	Yes, No
Serum potassium at baseline	<= 4.5, >4.5 or <=median, >median
Use of potassium binder at baseline	Yes, No
Use of angiotensin-converting enzyme inhibitors (ACEi) or angiotensin receptor blocker (ARB) at baseline	Yes, No
Systolic blood pressure at baseline	≤ median, > median
Dialysis vintage	≤ median, > median
Haemodiafiltration	Yes, No

3.3.5 Sensitivity analysis

The following sensitivity analyses will be performed on the primary composite endpoint:

- **Analysis using the PP analysis set**

- **Informative censoring**

In the primary survival analysis, renal transplantation could prevent the observation of the primary endpoint, and therefore is an informative censoring.

Renal transplant patient characteristics will be described. In addition, time to renal transplantation will be analysed to identify if this censoring process changes the “at risk” population in the primary survival model. Hence a competing risk framework could be used to verify the impact on the model estimations.

3.3.6 Exploratory analysis

- **Impact of the COVID-19 period on primary composite endpoint and CV death survival plots according to the date of onset of the epidemic period, according to international guidance’s:**

European Medicines Agency. Guidance on the management of clinical trials during the COVID-19 (coronavirus) pandemic. April 2, 2021 (version 4). https://ec.europa.eu/health/sites/health/files/files/eudralex/vol-10/guidanceclinicaltrials_covid19_en.pdf (22 April 2021).

US Food and Drug Administration. FDA guidance of conduct of clinical trials of medical products during COVID-19 public health emergency. March 2020 (Updated January 27, 2021). <https://www.fda.gov/media/136238/download> (17 February 2021).

A complementary analysis of exposure to COVID-19 infection could be performed adjusting the primary endpoint model on a time-dependent covariate “exposed/non-exposed COVID-19 patients” with 01/01/2020 as first exposed time. An effect of interaction between randomised treatment group and the time dependant covariate will be assess in the model.

- Investigator-reported (non-adjudicated) primary endpoint events

Expanded MACE events as reported by the investigators, independent from the critical event committee adjudication process

3.4 Secondary efficacy analysis

Statistical analysis of the secondary endpoints will be performed on the Intent-to-treat population. Secondly, the same analyses will be repeated on the per-protocol population.

3.4.1 Secondary endpoint part 1

To handle the multiple testing, outcomes will be analyzed using a hierarchical testing procedure until the p-value equals or exceeds 0.05, the primary outcome being the most important outcome, followed by the secondary outcomes ranked according to the importance order shown in below. The secondary objective will be considered by comparing the effects of spironolactone to placebo on: Composite of (1) death from any cause and (2) time to CV non-fatal event (hospitalisation for heart failure or non-fatal MI or acute coronary syndrome or non-fatal stroke) both at 2 years.

A composite endpoint, Finkelstein-Schoenfeld z score [8], is based on a combination of 1) all-cause mortality and 2) time to CV non-fatal events, both at 2 years, assuming a hierarchy of the two endpoints. Each patient i is compared to each patient j of the clinical trial in a pairwise manner and assigned a score, u_{ij} , of -1, 1 or 0, depending on whether the outcome is unfavourable, favourable or indeterminate in the hierarchy of outcomes. Thus, if patient i died before patient j , the score is -1; if patient j died before i , the score is 1. If it cannot be determined which patient died first (e.g., because of equality or censoring), then the second outcome (time to CV event) is compared and assigned a value of 1 or -1 depending on whether patient i has a better outcome or not. When it cannot be determined whether a patient has a more favourable outcome than the other (equality or censor at 2 years), then the score is assigned a value of 0.

The Finkelstein-Schoenfeld z score is based on the sum of patient scores in the experimental arm, and this statistical test assesses significant differences on the composite endpoints.

« Unmatched WinRatio » [9] estimates the effect of experimental treatment on the composite endpoints, death from any cause and time to CV event (excluding death) both at 2 years. For pairs of patients, each patient in the experimental arm is compared to each of the other patients in the standard arm. The WinRatio is the ratio of the number of winners (pairs in which the patient in the experimental treatment has a better outcome and the number of losers (pairs where the patient in the experimental treatment has a worse outcome. The 95% confidence intervals for the win ratio can be computed using Bootstrap (SAS macros are available from [contact], WinRatiofinal.sas and WinratioFinal_bootstrapFinal.sas [Finkelstein and al., Pocock and al.] or a R package is available).

Conditional on a sufficient number of patients in each centre (randomisation stratification variable), a stratified win ratio statistic could be calculated [10].

A sensitivity analysis of the winratio will include events occurring after 2 years of follow-up.

Components of the winratio:

Each component of this composite endpoint to the overall treatment effect will be examined. Methods similar to those described for the primary analysis will be used to analyse time to all-cause death and time to CV event.

In addition, an analysis similar to the primary analysis will assess and illustrate the impact of the COVID-19 period on the all-cause death survival plot according to the date of onset of the epidemic period.

A sensitivity analysis of time to all cause death endpoint will be performed with no censoring at the renal transplantation.

Additional secondary endpoints will be considered for hypothesis raising

3.4.2 Secondary endpoint part 2-a

Analyses similar to the primary composite endpoint analysis will be performed to analyse the time from randomisation to the first occurrence of death from a non-CV cause.

3.4.3 Secondary endpoint part 2-b

The cumulative rate of multiple non-fatal events comprising the primary outcome events: hospitalisation for heart failure or non-fatal MI or acute coronary syndrome or non-fatal stroke and occurrence of death i) from any cause, ii) from a CV cause, iii) from a non-CV cause.

The primary endpoint considers five distinct events; however, in each patient, multiple events may occur over time. Thus, the effect of treatment on the cumulative rate of events may be estimated taking into account the recurrence of events (and not only the first event). The number of events per patient will be described and compared using usual quantitative statistics.

Conditional to the cumulated number of adjudicated MACE events per patient, a survival analysis, i.e. the independent increment model of Anderson and Gill [5, 7], is an approach to analyse recurrent events. The model of Anderson and Gill is an extended Cox model that is a regression of the intensity of a recurrent event. The effect of treatment on the cumulative rate of events can be estimated with its statistical significance (Wald test). This analysis can be performed with adjustment on the “centre” variable and other variables.

3.4.4 Secondary endpoint part 2-c

Survival time without a major cardiovascular event: non-fatal MI, acute coronary syndrome, hospitalization for heart failure, non-fatal stroke, or cardiac arrest resuscitation (Diagnostic or MedDRA codage, EI_date (Table EI)) will be analysed using a similar methodology to that of the main analysis of the primary composite endpoint. .

3.4.5 Secondary endpoint part 2-d, part 2-e and part 2-g

- Incidence of procedures related to a stenosis or thrombosis of the vascular access for haemodialysis (Diagnostic or MedDRA codage, EI_date (Table EI))
- Incidence of coronary or peripheral revascularisation (including lower limb amputations) (Diagnostic or MedDRA codage, EI_date (Table EI))
- incidence of complete atrial fibrillation arrhythmia (Diagnostic or MedDRA codage, EI_date (Table EI))

The incidence and number of each procedure for stenosis or thrombosis at the site of vascular access for dialysis and the incidence of any coronary or peripheral revascularisation (among lower limb amputations) will be described using the “usual statistics”.

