1.3.5 Chronological sequence

Eligible patients having signed the consent form participate in the one-month run-in phase after which they were randomised conditional to the absence of hyperkalaemia ≥ 5.5 mmol/l on two occasions or on the day of randomisation or of serious adverse events.

The included and randomised patients participate in the study for a duration of 2 years on average, the latter of which can be amended by the Steering Committee in light of the rate of event occurrences. The study was completed when the number of incidents necessary for attaining a sufficient power has been observed. Blinding was lifted only in the case of a serious adverse event in which care management may be modified according to the treatment received by the patient: spironolactone/placebo; patients were followed until the end of the study.

Figure 1: Scheme of the study

Figure 1: ALCHEMIST trial design

(*): dosage of 25 mg/eod; patients presenting blood potassium > 5.5 mmol/l on two occasions will be excluded before randomization;
 (**): maximum dosage of 25 mg/d; could be reduced or temporarily suspended if blood potassium is > 5.5 mmol/l;
 From V1 to V12: Other visits will be scheduled if blood potassium is > 5.5 mmol/l.

Summary table of visits.

	Visit 1 W-4	Visit 2 W-2	Visit 3 D0	Visit 4 W+2	Visit 5 W+4	Visit 6 à 13 M3 to M24
Verification of the selection criteria	x					
Verification of the inclusion/exclusion criteria						
Pregnancy test (if applicable)	x					
Information/Informed consent	x					
Physical examination	x	x	x	x	x	x
ECG	x					
Dispensing of medication	x		x		x	x
Self-questionnaires on quality of life	x					x (**)
Randomisation			x			
Blood potassium	3/week	3/week	3/week	3/week	x	x
Verification of compliance		x	x	x	x	x
Dosage increase		x	x	x	x	x
Dosage adjustment (if necessary)				x	x	x
Concomitant treatments	x					x
SAEs		x	x	x	x	x

(**) only at V6, V9, V13, V17 and V21

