3.1 General issues for statistical analyses

Statistical software

All statistical analyses will be performed using SAS® Software version 9.4 in a Windows environment, or R software version 3.6.3.

Missing data and outliers

All efforts will be made to collect outcome data including in patients withdrawn from the trial for whichever reasons and to minimise the amount of missing data. Unless specifically indicated, missing data will not be replaced. Outliers will be discussed as to whether to be kept or set as missing prior to database lock.

Stratification and centre effect

Unless otherwise specified, the treatment effect will be estimated on the primary and secondary outcomes after adjustment on the stratification variable.

Data transformation

Analysis of continuous variables may require transformation to normalise the distributions if the latter is justified to fulfil the hypotheses of the statistical methods to be used.

Derived and computed variables

Calculated delays since randomisation will be calculated as the time elapsed since the day of randomisation (day zero).

Delays will be converted in years or months by dividing the delays by 365.25 days or 30.4375 days respectively.

Duration=Delay+1 (days)

For the patient's date of birth, if no day is entered then it will all be replaced by 15.

Some derived and computed variables (such as delays) have been initially identified, and are described later in the document. It is expected that additional derived variables may be required. The SAP will not be amended for additional variables that are not related to the primary target or key secondary target variables. Any additional derived or computed variables will be identified and documented in the SAS programs that create analysis files.

Usual statistical presentations and tests

Description of continuous variables includes the mean, standard deviation, median, 1st and 3rd quartile, and range.

Description of categorical variables includes the frequency and percentage (based on non-missing values). Description of ordered variables includes the frequency, percentage and cumulative percentage.

Unless otherwise specified, between-group differences will be tested using the Wilcoxon rank-sum test for quantitative outcomes (or Student's t-test in case of normal distribution), using Fisher's exact test for binary outcomes, and the Mantel-Haenszel Chi-square test for ordinal outcomes.

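### Section 3.4.5 summarises vascular-access procedures and revascularisation without time at risk and names no method for atrial fibrillation, so longer survival on spironolactone would modestly distort these comparisons

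*SAP*

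**What the plan says.** Section 3.4.5 lists three endpoints as incidences: vascular-access procedures (2-d), coronary or peripheral revascularisation (2-e) and atrial fibrillation (2-g). Each is tied to an event date in the adverse-event table. One method sentence follows. It says that "The incidence and number of each procedure for stenosis or thrombosis at the site of vascular access for dialysis", and the incidence of any revascularisation, will be described with the usual statistics. Atrial fibrillation is not in that sentence.

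Section 3.1 sets out the usual statistics as frequency and percentage for categorical variables and means and quantiles for continuous ones. Unless otherwise specified, "between-group differences will be tested using the Wilcoxon rank-sum test for quantitative outcomes" (or a t-test), and Fisher's exact test is used for binary outcomes. The same part of 3.1 has a Kaplan-Meier line for survival estimation, which is not tied to any of these three endpoints.

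Follow-up has no fixed length. Section 1.3.5 gives 2 years on average, open to amendment, and states: "The study was completed when the number of incidents necessary for attaining a sufficient power has been observed". The quality-of-life SAP gives an average of 4 years.

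Section 3.4.3 (endpoint 2-b) says, without condition: "The number of events per patient will be described and compared using usual quantitative statistics". It then offers an Andersen-Gill model, conditional on the number of events.

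**The concern.** A percentage or a count per patient gives a patient who dies early the same weight as one followed to the end. That is harmless if both arms have the same time at risk. Here time at risk may depend on treatment: the trial tests whether the drug reduces a composite that includes cardiovascular death, and the SAP's introduction quotes 29% mortality at 2 years. An arm that survives longer has more time in which to have an access procedure or a revascularisation, and its crude figures rise even if the underlying rate is identical.

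Other event endpoints in the same plan do not have this gap. Endpoints 2-a and 2-c follow the time-to-event methods of the primary analysis, 2-b has the Andersen-Gill option, and 2-h names time to first and recurrent events. At stake is the reading of three hypothesis-raising endpoints: a neutral effect could look slightly unfavourable, or a true benefit could look smaller than it is.

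**Working it through.** **The plan's own figure.** The SAP gives no figure for 2-d, 2-e or 2-g, so only its sample size can be reproduced. Section 1.3.4 assumes "An annual event probability of events of 0.18 in the placebo arm" and "A 30% reduction of this annual event probability in the spironolactone arm (active treatment), hence a probability of 0.126". The implied hazard ratio is ln(1 − 0.126)/ln(1 − 0.18) = 0.679. With two-sided 5% and 80% power, Schoenfeld's formula gives 209 events. The mean 2-year event probability is (0.3276 + 0.2361)/2 = 0.2819, so N = about 742, against 750 stated. The 30% effect used below is therefore read as the plan uses it: it applies to the primary composite, not to all-cause death.

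**Inputs for the exposure check**
- Mortality of 29% at 2 years (SAP section 1): placebo hazard μ0 = −ln(0.71)/2 = 0.171 per year.
- Cardiac share of deaths, 42% (SAP section 1).
- Assumed lower case: a 30% reduction confined to that share, all-cause HR = 1 − 0.42 × 0.30 = 0.874. (That 0.42 × 0.30 equals the planning probability of 0.126 is a coincidence.)
- Assumed upper case: all-cause HR 0.70, which the SAP does not state.
- Assumed: constant hazards, no drug effect on the event itself, event hazard λ from 0.03 to 0.30 per year.
- Horizons: 2 years (main SAP) and 4 years (quality-of-life SAP).

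**Formulas**
- Mean time at risk per patient: E = (1 − exp(−μT))/μ. With equal event rates, the ratio of mean counts is E1/E0.
- Crude proportion with an event: λ/(λ + μ) × (1 − exp(−(λ + μ)T)).

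**Results (true rate ratio 1.00 throughout)**

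| Horizon | All-cause HR | Years at risk, placebo vs spironolactone | Count ratio | Proportion ratio, λ 0.03 to 0.30 | Proportions at λ = 0.10 |
|---|---|---|---|---|---|
| 2 y | 0.874 | 1.693 vs 1.728 | 1.021 | 1.018–1.020 | 15.4% vs 15.7% |
| 2 y | 0.70 | 1.693 vs 1.778 | 1.050 | 1.045–1.050 | 15.4% vs 16.2% |
| 4 y | 0.874 | 2.896 vs 3.010 | 1.039 | 1.031–1.038 | 24.4% vs 25.3% |
| 4 y | 0.70 | 2.896 vs 3.178 | 1.097 | 1.077–1.095 | 24.4% vs 26.6% |

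A person-time rate ratio or cause-specific hazard ratio would be 1.00 in every row.

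**Robustness.** Adding an assumed transplant hazard of 0.05 per year to both arms leaves the count ratios at 1.020 and 1.049 (2 years) and 1.038 and 1.094 (4 years). Using the SAP's 52% mortality at 5 years instead (μ0 = −ln(0.48)/5 = 0.147) gives 4-year count ratios of 1.034 and 1.084.

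**Chance of a spurious result.** With 375 per arm, the chance of a nominal p < 0.05 against the drug is 3% to 7% at 2 years. At 4 years it reaches 21% in the most extreme case (HR 0.70, λ = 0.30). Without distortion it is 2.5%.

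**If the drug does help.** Suppose it lowers the event hazard by 10% (λ = 0.10, 2 years). With equal survival the crude proportion ratio would be 0.91. With the two survival assumptions it becomes 0.93 (HR 0.874) and 0.95 (HR 0.70): attenuated, but still favourable.

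**The case against.** Several points on the other side are sound.

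- **The text may be under-specified rather than fixed on crude methods.** Section 3.1 includes Kaplan-Meier, 3.4.5 cites event dates, and 3.4.7 applies the usual statistics directly under items labelled as time to first and recurrent. This softens the reading but does not remove it, since nothing assigns a time-based method to 2-d, 2-e or 2-g.
- **Section 3.4.5 only describes.** Sections 3.4.3, 3.4.6 and 3.4.7 add a comparison; 3.4.5 does not. The tests reach these endpoints only through the 3.1 default. A crude percentage shown by arm carries the same shift, tested or not.
- **Part of this is a choice of estimand.** The crude-proportion formula above is the cumulative incidence at T with death as a competing event. A cumulative incidence curve would show the same ratios. It is a legitimate description of absolute risk, but it does not isolate an effect on the event rate. The objection to crude methods is stronger for counts per patient.

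A reader might also infer more than the documents support:

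- **That spironolactone will look worse.** This needs a real survival benefit and little or no effect on these events. The plan hypothesises an effect on the composite, not an all-cause mortality HR of 0.70.
- **That the plan prescribes crude percentages for atrial fibrillation.** Section 3.4.5 prescribes nothing for it; the omission is a gap of its own.
- **That event-driven closure is itself biasing.** Calendar follow-up is balanced by randomisation. Only differential death or transplantation shifts the comparison.
- **That 3.4.3 has the same defect throughout.** Its Andersen-Gill model uses time at risk; only the unconditional count comparison does not.

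**Conclusion.** The point holds as a modest weakness of method. For 2-d and 2-e the stated summaries ignore time at risk, and for 2-g no method is stated. If the drug prolongs survival and leaves these events unchanged, its mean counts are inflated by about 2% to 5% at 2 years and 4% to 10% at 4 years, with proportions slightly less affected. The upper ends rest on an all-cause HR of 0.70; the lower ends, on a benefit confined to the cardiac share of deaths, stay closer to the plan's own figures. All values assume constant hazards. If the drug has no effect on survival and transplantation is balanced, there is no shift. The endpoints lie outside the testing hierarchy and are labelled hypothesis-raising, so no primary or hierarchical conclusion changes. The correction is still worth making, because it is cheap and brings 3.4.5 into line with its sibling endpoints.

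**What to change.** - **Section 3.4.5, first events.** Analyse the first event of 2-d, 2-e and 2-g, naming atrial fibrillation explicitly, as time from randomisation. Use the Cox model of 3.3.2 as a cause-specific model, with the censoring of 3.3.1 (transplantation, death, end of study). State that death from any cause censors here, since cardiovascular death is not an event for these endpoints.
- **Section 3.4.5, total events.** Report rates per 100 patient-years and compare them with a count model that has a follow-up offset, for example negative binomial.
- **Absolute risk.** Cumulative incidence with death and transplantation as competing events may be shown as description. It does not remove the survival effect, so the treatment comparison should rest on the cause-specific hazard ratio or the rate ratio.
- **Section 3.4.3.** Keep the Andersen-Gill model and give the unconditional events-per-patient comparison as a rate per patient-year.

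The cost is a few lines of SAP text and a little more programming on dates already in the database. No new data are needed.
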